### **5.4 Treatment masking**

This is an open-label study and neither Investigators nor patients are masked.

### **5.5 Treating the patient**

#### **5.5.1 Subject numbering**

Each patient is uniquely identified in the study by a combination of his/her center number and subject number. The center number is assigned by Novartis to the investigative site. Upon signing the informed consent form, the patient is assigned a subject number by the Investigator. At each site, the first patient is assigned subject number 01, and subsequent patients are assigned consecutive numbers (e.g. the second patient is assigned subject number 02, the third patient is assigned subject number 03). Once assigned to a patient, the subject number will not be reused. This also applies to the situation in which a patient has initially failed screening but at a later stage meets all eligibility criteria. It is then possible to re-screen the same patient but a new subject number has to be assigned. As long as the recruitment phase has not yet ended, re-screening (on one occasion only) is possible.

The site should enter the data into the eCRF for that patient using the individual subject number. Only the assigned subject number should be entered in the field labeled "Patient ID" on the eCRF data entry screen (e.g. enter '01', '02', etc.). If the patient undergoes screening but fails to meet the eligibility criteria, the reason(s) will be entered on the Screening Log and the Demography eCRF should be completed.

If the patient is eligible for treatment but fails to be treated at the Baseline visit for any reason, the reason(s) for not being treated should be entered on the Screening Log and the Demography eCRF should be completed. Re-screening (on one occasion only) may be possible for these patients.

## **5.5.2 Dispensing the investigational treatment**

Within each participating country, each study site will be supplied by Novartis with investigational treatment (study drug) in commercially available packaging, labelled according to local legal requirements. The decision to administer study drug to the patient is made according to the protocol specified treatment regimen.

### **5.5.3 Handling of study treatment**

#### **5.5.3.1 Handling of investigational treatment**

Investigational treatment (study drug) must be received by a designated person at the study site, handled and stored safely and properly, and kept in a secured location to which only the Investigator and designees have access. Upon receipt, all investigational treatment should be stored according to the instructions specified on the labels. Clinical supplies are to be dispensed only in accordance with the protocol. Technical complaints are to be reported to the respective Novartis CPO Quality Assurance.

Medication labels will be in the local language and comply with the legal requirements of each country. They will include storage conditions for the investigational treatment but no information about the patient.

The Investigator must maintain an accurate record of the shipment and dispensing of investigational treatment in a drug accountability log. All used vials/PFS packaging should be kept until monitoring of drug accountability has been completed by the field monitor. Monitoring of drug accountability will be performed by the field monitor during site visits and at the completion of the trial.

At the conclusion of the study, and as appropriate during the course of the study, the Investigator will return all unused investigational treatment, packaging, drug labels, and a copy of the completed drug accountability log to the Novartis monitor or to the Novartis address provided in the Investigator folder at each site.

#### **5.5.3.2 Handling of other study treatment**

Not applicable.

#### **5.5.4 Instructions for prescribing and taking study treatment**

For the entire trial, ranibizumab should be administered in the study eye on the day of the scheduled study visit. In the event that a protocol specified ranibizumab injection into the study eye is delayed for more than 7 days following the scheduled study visit, a protocol deviation will be recorded but the patient may continue in the study. The assessments required as part of an Unscheduled Visit should be conducted and recorded in the eCRF (see Section 6). The Investigator should make every effort to resume the protocol specified timings for scheduled study visits and simultaneous ranibizumab injections to the study eye. Repeat ranibizumab injection into the study eye may not be administered sooner than 23 days after the last ranibizumab injection into the study eye.

Instructions on how to prepare and administer ranibizumab for IVT injection using the PFS or vial should follow the locally approved product information leaflet. Details of all PFS and vials administered will be recorded in the eCRF. Standard local practice should be applied in the peri-injection management of patients and should be consistent with the local labelling and/or IB.

The injection procedure should be carried out under aseptic conditions, which includes the use of surgical hand disinfection, sterile gloves, a sterile drape and a sterile eyelid speculum (or equivalent) and the availability of sterile paracentesis (if required). Adequate anesthesia and a broad-spectrum topical microbicide to disinfect the periocular skin, eyelid and ocular surface may be administered prior to the injection, in accordance with local practice. The injection needle should be inserted 3.5-4.0 mm posterior to the limbus into the vitreous cavity, avoiding the horizontal meridian and aiming towards the center of the globe. The injection volume of 0.05 ml is then delivered; a different scleral site should be used for subsequent injections. Both intraocular pressure and the perfusion of the optic nerve head must be monitored and managed appropriately following IVT injection of ranibizumab.

##### **5.5.4.1 Monthly Treatment Period: Day 1 to Day 60**

After eligibility confirmation at Baseline (Day 1), all patients will receive IVT injection of ranibizumab into the study eye. Re-treatment with IVT injection of ranibizumab will occur on Day 30 and Day 60.

#### **5.5.4.2 PRN Treatment Period: Day 90 to Day 180**

All patients will have monthly assessments of BCVA and disease activity assessed by OCT. These assessments, together with an assessment of the patient's visual symptoms, will be used for the decision of potential re-treatment with ranibizumab. This PRN regimen, will permit re-treatment with ranibizumab at Day 90, Day 120 and/or Day 150 if in the opinion of the Investigator persistent or worsening visual symptoms are attributed to nAMD, and/or if there is evidence of worsening ETDRS best corrected visual acuity (>1 letter decline since last Study Visit) and/or the presence of persistent or worsening disease activity on OCT\*. Source documentation must provide evidence for one or more of these retreatment criteria.

#### **5.5.4.3 Treatment of the Fellow Eye**

Patients who develop visual impairment due to nAMD in the fellow eye (non-study eye) during the study that, in the Investigator's opinion, qualifies for and requires treatment, may be treated at the Investigator's discretion according to the standard of care, including ocular administration with ranibizumab. This eye is then called the fellow treated eye.

Ranibizumab will be provided by the Sponsor (supplied for investigational treatment) and should be administered according to the SmPC or local labelling. Details of all PFS and vials administered will be recorded on drug accountability forms and a record of the administration also included in the eCRF.

Treatment of the fellow eye must be scheduled in a way not to disturb the schedule for visits and treatments of the study eye. Ideally injection of the fellow eye should occur on the same day as a scheduled study visit in order to minimize the total number of clinic visits required by the patient. Bilateral IVT injections of ranibizumab may occur at any scheduled study visit between Day 30 and Day 150. The fellow treated eye must be monitored according to routine practice and AE(s) and SAE(s) must be captured in the eCRF. Should injection of the fellow eye occur at a visit other than a scheduled study visit, this should be recorded in the eCRF as an unscheduled study visit and all protocol specified procedures for an unscheduled visit should be completed (see Section 6).

If in the Investigator's opinion, the fellow eye requires further treatment with ranibizumab, this should not occur more frequently than monthly in accordance with the posology section of the SmPC. A protocol deviation will be recorded should the patient receive a repeat ranibizumab injection into the fellow eye less than 23 days after the previous injection into the fellow eye. However, the patient will not be withdrawn from the study.

At the time when treatment of the fellow eye is being initiated, the BCVA assessment for the fellow eye should be repeated and recorded in the eCRF.

Treatment with other anti-VEGF medication other than ranibizumab is prohibited in either eye at any time during the study.

---

\* Persistent or worsening disease activity on OCT includes the presence of sub-retinal fluid, persistent or increased number, size or total volume of IRC, or increased central retinal or foveal thickness, or similar quantitative retinal imaging data recorded within the individual patient record.

Treatment for non-nAMD indications with anti-angiogenic drugs including ranibizumab in the fellow eye is prohibited.

### **5.5.5 Permitted dose adjustments and interruptions of study treatment**

Dose adjustments, i.e., adjustments of the injection volume of ranibizumab dose solution, are not permitted. Adjustments of the PRN dosing regimen of ranibizumab that is described as part of the study treatment administration in Section 3.1, and Section 5.5.4 are not permitted.

Ranibizumab treatment should be withheld and treatment should not be resumed earlier than the next scheduled treatment in the event of:

- an IOP of  $\geq 30$  mm Hg,
- an untreated retinal tear is diagnosed,
- active or suspected ocular or periocular infections,
- active severe intraocular inflammation.

### **5.5.6 Rescue medication**

No rescue medication is permitted in this study.

### **5.5.7 Concomitant treatment**

The Investigator should instruct the patient to notify the study site about any new medications he/she takes after the patient was enrolled into the study. All medications (including for non-ophthalmic conditions), procedures and significant non-drug therapies (including physical therapy and blood transfusions) administered after the patient was enrolled into the study must be recorded in the eCRF.

Medications that may be used as part of the protocol specified retinal image acquisition (e.g., mydriatic drops, fluorescein dyes) and pre- and post-injection medications (e.g., topical anesthetics, topical antimicrobials) used by a patient during the study, are not considered concomitant medications.

If a patient requires intraocular surgery on the study eye during the course of the study, the patient should be withdrawn from the study.

### **5.5.8 Prohibited Treatment**

Use of treatments, as displayed in Table 5-1 is NOT allowed after the Screening visit and for the duration of the study. In addition, there are certain wash-out periods to be respected as outlined in the list of exclusion criteria.

Please see Table 5-1 below for actions to be taken, apart from stopping the prohibited medication taken.

**Table 5-1 Prohibited treatment**

Medication	Action to be taken
Anti-VEGF drugs other than ranibizumab (ocular or systemic)	Withdraw patient from study
Intra- or periocular corticosteroids (including sub-tenon but excluding topical formulations) – study eye only	Withdraw patient from study
Intra-ocular corticosteroid implants – study eye only	Withdraw patient from study
Investigational drugs and interventions of any type	Withdraw patient from study

### 5.5.9 Discontinuation of study treatment

Patients may voluntarily discontinue study treatment for any reason at any time.

The study and treatment completion dates will be determined by the last visit the patient came to the clinic.

The Investigator must provide follow-up medical care for all patients who are prematurely withdrawn from the study, or must refer them for appropriate ongoing care. Patients who are prematurely withdrawn from the study will not be replaced by an equal number of newly enrolled patients.

Patients can discontinue study treatment because of the appearance of a new health condition suspected to require appropriate care or require medications prohibited by the protocol (Section 5.5.8), unacceptable AEs, refusal to continue treatment, or at the Investigator's discretion based on his or her clinical judgment.

The Investigator should discontinue study treatment for a given patient or withdraw the patient from study if, on balance, he/she believes that continuation would be detrimental to the patient's well-being.

Study treatment must be discontinued under the following circumstances:

- Withdrawal of informed consent
- Emergence of the following AEs:
  - Stage 3 or 4 macular hole
  - Stroke or transient ischemic attack
  - Rhegmatogenous retinal detachment
- Pregnancy
- Use of prohibited treatment in Table 5-1
- Two sequential ranibizumab injections to the study eye should have occurred according to the protocol specified monthly/PRN treatment period criteria but were withheld (see Section 5.5.5) or missed.

- Any other protocol deviation that results in a significant risk to the patient's safety.

Patients who permanently discontinue study treatment and start a prohibited non-study treatment (see Section 5.5.8) should be withdrawn from the study and undergo all assessments for End of Study visit as described in Table 6-1 and Table 6-2.

Patients who discontinue study treatment but do not receive prohibited treatment should not be considered withdrawn from the study and may continue their scheduled follow-up assessments until End of Study.

The Completion/Withdrawal eCRF page should be completed, providing the primary reason for stopping study treatment.

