### **PRN treatment period: Day 61 to Day 180**

Efficacy and safety assessments will be repeated (see Table 6-1) at Day 90, 120, 150 and 180. All subjects will attend Scheduled Study Visits every 30 ( $\pm 7$ ) days. The primary endpoint will be evaluated when patients have completed assessments at the Day 90 visit.

Between the Day 90 and Day 150 visits inclusive, the decision to administer ranibizumab 0.5mg will be at the discretion of the Investigator and driven either by persistent or worsening visual symptoms attributed by the Investigator to nAMD, or worsening visual acuity ( $>1$  letter decline since last Study Visit) or by the presence of persistent or worsening disease activity on OCT\*. Source documentation must provide evidence for one or more of these retreatment criteria. Injections of IVT ranibizumab to the study eye, where required, should occur on the same day as the scheduled study visit.

Final efficacy and safety assessments will be conducted at Day 180.

---

\* Persistent or worsening disease activity on OCT includes the presence of sub-retinal fluid, persistent or increased number, size or total volume of IRCs, or increased central retinal or foveal thickness, or similar quantitative retinal imaging data recorded within the individual patient record.

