### **3.3 Rationale of dose/regimen, route of administration and duration of treatment**

In this study, ranibizumab will be administered at the SmPC and other product labels approved dose of 0.5mg and the dosing regimen is consistent with current clinical practice where re-treatment decisions are based not only on changes in VA but also on retinal morphology changes that may be indicative of disease activity (Myolonas 2009). Historical data from a number of clinical trials demonstrate that 0.5mg ranibizumab offers a favorable benefit-risk profile. Ranibizumab is administered as an IVT injection to maximize the bioavailability of the drug at the site of pathology while minimizing systemic exposure.

The posology section of the SmPC for ranibizumab recommends monthly injections until maximum visual acuity is achieved with additional injections thereafter in the event of a loss of visual acuity due to nAMD. In this study, this re-treatment criterion will be applied although in addition re-treatment will occur based on measures of increasing or persistent retinal disease activity as these are commonly used in clinical practice. The permitted interval between ranibizumab injections will be 23 to 37 days during the Monthly Treatment period and 23 days or greater during the PRN Treatment period. This study design is in keeping with the posology used in other prospective studies with ranibizumab in nAMD.

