**Table 6-2 Assessment schedule (peri-injection procedures, safety assessments and venous blood sample collection)**

	Screening V1	Baseline V2	V3	V4	PEV V5	V6	V7	EOS or EWW V8	UNSCHED V
Dispense topical antibiotic medication according to local practice		(X)	(X)	(X)	(X)	(X)	(X)		
Ranibizumab injection		X	X	X	(X)	(X)	(X)		
Post-injection assessments		X	X	X	(X)	(X)	(X)		
Vital signs	X	X	X	X	X	X	X	X	X
Height and Weight	X								
Adverse events	X	X	X	X	X	X	X	X	X
PEV: Primary Endpoint Visit. EOS: End of Study visit also incorporates the Early Withdrawal Visit (EWW). UNSCHED V: Unscheduled visit (X) Indicates that local standard practice should be applied or in the case of ranibizumab injection, that Investigator judgment is used to determine whether repeat injection is required.									

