## **Compliance to treatment regimen**

The evaluation of compliance will assess whether ranibizumab injections were administered according to the protocol specified regimen during the monthly treatment period and according to the Investigator's assessment of disease activity during the PRN treatment period.

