2.1.7 Treatment exposure

Treatment exposure to ranibizumab will be summarized by subgroup and overall for the SAF, and will include:

- Duration of exposure to ranibizumab for both study eye and fellow treated eye, as well as total duration of exposure (study eye and fellow eye). Duration of exposure will be calculated as date of last ranibizumab injection – date of first ranibizumab injection + 1, for study eye, fellow treated eye and both eyes together
- Total number of injections overall the study course and number of injections by visit (including unscheduled visits), for both study eye and fellow treated eye
- Number and percentage of patients who received bilateral injections of ranibizumab (both the study eye and fellow eye injected at the same visit) by visit
- Reason for PRN treatment (BCVA decline, or OCT criteria) by visit during the PRN treatment period, for study eye
- Reason for no dosing by visit, for study eye. Prior to database lock, a complete list of reasons for no dosing during the Monthly treatment period, as recorded on the eCRF, will be provided by ██████ to Novartis in an Excel spreadsheet. Novartis will review them and classify them as ocular or non-ocular.
- Compliance to treatment regimen, for study eye

Compliance to treatment regimen will be assessed as follows

- Monthly treatment period, compliance= $100 * (\text{number of injections in study eye} / 3)$
- PRN treatment period, compliance= $100 * (\text{number of injections done in study eye} / \text{number of required injections in study eye based on changes in patient symptoms, BCVA or OCT})$

An injection will be considered as required if:

- in the opinion of the Investigator persistent or worsening visual symptoms are attributed to nAMD and/or
- there is evidence of worsening early treatment diabetic retinopathy study (ETDRS) BCVA (>1 letter decline since last Study Visit) and/or
- the presence of persistent or worsening disease activity on OCT (presence of sub-retinal fluid, persistent or increased number, size or total volume of IRC, or increased central retinal or foveal thickness)

All treatment exposure to ranibizumab details, including derived variables, will be listed.

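### The protocol leaves PRN injection to investigator judgment, but the SAP counts an injection as required whenever the BCVA or OCT criterion is met, and section 5.5.9 does not say whether a declined injection is a missed one.

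*Protocol*

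**What the plan says.** **Passages that leave the decision to the investigator**

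- Protocol 3.1, PRN treatment period: from Day 90 to Day 150 "the decision to administer ranibizumab 0.5mg will be at the discretion of the Investigator", driven by symptoms, a fall of more than 1 letter since the last visit, or OCT activity.
- Protocol 5.5.4.2: the regimen "will permit re-treatment with ranibizumab at Day 90, Day 120 and/or Day 150". The investigator's opinion is attached to the symptom criterion.
- Protocol Table 6-2, footnote: "Investigator judgment is used to determine whether repeat injection is required".
- Protocol 6.3: PRN compliance is whether injections were given "according to the Investigator's assessment of disease activity during the PRN treatment period".

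**Passages that treat a met criterion as an injection due**

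- SAP 2.1.7: "An injection will be considered as required if" any one of the three criteria is met. Investigator opinion appears only in the symptom criterion; the BCVA and OCT criteria carry no such term. The count of required injections is the denominator of PRN compliance.
- Protocol 3.3: "in addition re-treatment will occur based on measures of increasing or persistent retinal disease activity".
- Protocol 5.5.9: stopping study treatment is mandatory when two sequential study-eye injections "should have occurred according to the protocol specified monthly/PRN treatment period criteria but were withheld (see Section 5.5.5) or missed".

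Protocol 5.5.5, to which 5.5.9 refers, lists four reasons to withhold: raised IOP, an untreated retinal tear, infection, and severe intraocular inflammation. It also forbids adjustments of the PRN regimen.

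**The concern.** Take a patient whose BCVA has fallen by 2 letters at a PRN visit, where the investigator does not attribute the fall to active disease and decides not to inject. Section 3.1 allows that decision, and under 6.3 the visit is compliant because it follows the investigator's assessment. Under SAP 2.1.7 the same visit adds one to the required injections and nothing to those given. The Table 6-2 footnote and the SAP thus use the word *required* in opposite senses: in one, judgment settles it; in the other, the criterion does.

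The same gap touches a mandatory rule. If a site counts the decision as a missed injection, two in a row end study treatment; if it does not, treatment continues. Sites that read 5.5.9 differently would produce different exposure and different discontinuation counts for patients managed in the same way, and that would feed into the BCVA and CSRT results after Day 90.

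**Working it through.** The plan states no figure to reproduce here. The check is a comparison of the text, the SAP's own formula worked through, and a bound on how often the situation could arise.

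**1. Compliance under the SAP formula.** SAP 2.1.7 gives PRN compliance = 100 × injections given / injections required. Suppose a criterion other than symptoms is met at Days 90, 120 and 150, so that three are required:

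| Declined | Given | SAP 2.1.7 | Given / judged needed by the investigator (one reading of 6.3) |
|---|---|---|---|
| 1 | 2 | 100 × 2/3 = 66.7% | 2/2 = 100% |
| 2 | 1 | 100 × 1/3 = 33.3% | 1/1 = 100% |
| 3 | 0 | 100 × 0/3 = 0% | 0/0, not defined |

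The three visits are those named in 3.1, 5.5.4.2 and Table 6-2. Section 5.3 names only Days 90 and 120, and should be aligned at the same time.

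**2. Does 5.5.9 catch a declined injection?** The rule needs an injection that was due under the criteria and was then either withheld or missed. *Withheld* carries a cross-reference to 5.5.5, whose list contains safety findings only, so a discretionary decision is not covered by it. What remains is *missed*, which no passage defines. Whether the injection was due at all depends on whether a met criterion obliges or permits it, and that is the point on which the passages differ.

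**3. What a stop could remove.** If a declined injection did count, the pairs are:

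- Day 60 + Day 90: injections at Days 120 and 150 could be lost. Day 60 belongs to the fixed monthly schedule, so only the Day 90 decision is discretionary.
- Day 90 + Day 120: the Day 150 injection could be lost.
- Day 120 + Day 150: no scheduled injection is left.

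**4. How often the BCVA criterion is met by chance.** Assumption, not from the documents: a stable eye, BCVA in whole letters, measurement SD of 2.5 to 5 letters per visit. The difference between two visits has SD √2 × SD, and a fall of more than 1 letter means 2 or more, so with a continuity correction P ≈ Φ(−1.5 / (√2 × SD)).

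- SD 2.5: Φ(−1.5/3.54) = 0.336
- SD 5: Φ(−1.5/7.07) = 0.416

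A simulation of 400,000 eyes gives 0.336 to 0.417, that is 34–42% per visit. This is only the rate at which the criterion is met. Arriving at a number of declined injections would need the probability that the investigator then decides not to inject, and the documents give none.

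**The case against.** The strongest reply is that the passages can be read together. Section 3.1 says the decision is driven by the criteria, 3.3 says re-treatment will occur on measures of disease activity, and 5.5.5 forbids adjusting the PRN regimen. On that view, discretion means judging whether a criterion is met, and the SAP and 5.5.9 follow. This reading is arguable, but it does not settle the matter. A fall of more than 1 letter is a numerical fact that leaves nothing to judge, and 5.5.4.2 and the Table 6-2 footnote stay permissive.

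A second reply is that 5.5.9 does not reach a considered decision at an attended visit: *withheld* points to safety findings, and an injection the investigator judged unnecessary is not naturally called missed. This largely stands. A reader might infer that using discretion forces a treatment stop; the documents support that only as one possible reading of an undefined word.

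A third reply is that much of the remedy exists. Section 6.3 records the reason for dosing or not dosing, and SAP 2.1.7 summarises reasons for no dosing by visit. That is correct, and it makes the fix small. But the compliance formula does not use the recorded reason, and the SAP's planned review of those reasons before database lock covers the monthly period only.

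Finally, the SAP sets no compliance cut-off, so no patient is formally classed as non-compliant; a descriptive percentage falls. That also stands.

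**Conclusion.** The inconsistency is real and should be corrected. The firm part is compliance: SAP 2.1.7 can report 66.7%, 33.3% or 0% for care that section 3.1 allows, and its denominator does not match protocol 6.3. The weaker part is the stop rule: 5.5.9 is unclear, and the consequence attached to it is mandatory.

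The reach is limited. Efficacy is assessed before injection (protocol 6.4), so Day 90 CSRT is measured before any PRN decision and a reader should not infer that the primary endpoint value is affected. No FAS data are excluded for deviations, and patients who stop treatment without prohibited therapy may remain in follow-up. What can change is compliance, exposure, discontinuation counts and results after Day 90. Membership of the PPS, which requires that assigned treatment was followed, might also change, but the deviation list in SAP Appendix 2 is not available here, so this cannot be judged.

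A reader might also take the chance of meeting the BCVA criterion at two sequential PRN visits, 9–18% under the same SD assumption, as the share of patients stopped. It is not: it involves no declined injection, and it includes the Day 120 + Day 150 pair, after which nothing is left to lose. For Day 90 + Day 120 alone the simulation gives 4.7–9.6%, still before any decline rate. The number of affected patients is unknown.

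**What to change.** 1. Reconcile protocol 3.1, 3.3, 5.5.4.2, 5.5.5, 5.5.9, 6.3, Table 6-2 and SAP 2.1.7 so that all say the same on whether a met criterion obliges or permits an injection. The choice belongs to the sponsor's clinicians and is not made here.
2. Make the PRN compliance denominator in SAP 2.1.7 match protocol 6.3 as reconciled, and state how a patient with a denominator of zero is reported.
3. State in 5.5.9 whether *missed* includes a deliberate decision not to inject.
4. Use the existing dose/no-dose reason field to report, for the PRN period, three separate categories: criterion met and investigator decided not to inject; withheld under 5.5.5; and missed. This also supplies the rate of declined injections that is now unknown.

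The cost is a clarifying protocol amendment, SAP wording and at most one added response option in the eCRF. No new assessment and no change in sample size is needed.
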